		
 • Moderate (abnormal albumin or abnormal bilirubin) • Advanced (abnormal albumin and abnormal bilirubin) 
The primary efficacy endpoint will also be assessed for the following clinically relevant subpopulations.
 
 • Monotherapy in patients who are intolerant or non-responsive to UDCA • Elderly patients 
Assuming a strong correlation between biochemistry and clinical outcomes using the total study population (Section 13.1.5.1) is observed, we will further assess the biochemical improvement in relevant subpopulations as applicable (eg, Rotterdam disease severity and monotherapy) and estimate the reduction in risk of clinical outcomes associated with the biochemical improvement.
 
Additional details regarding statistical methods and subgroup definitions will be provided in the SAP.
	
This analysis will provide additional insight into the connection between surrogate endpoints and clinical outcome events allowing for evaluation of benefit in subpopulations for which the study is not powered.

Section 13.1.12 Continuous Monitoring and Interim Analyses
	
Both interim analyses will be pre-specified and will occur after accrual of 50% and 75% of clinical outcome events, respectively.
 
The DMC will review the available efficacy data in conjunction with detailed safety data and other relevant information to recommend continuation, modification, or cessation (for efficacy or futility) of the study beyond each interim analysis.
	
Both interim analyses will be pre-specified and will occur after accrual of 50% (64 events) and 75% (96 events) of clinical outcome events, respectively.
 
The DMC will review the available efficacy data in conjunction with detailed safety data and other relevant information to recommend continuation,
	
Added number of anticipated events.
 
Clarification

Section	Original Text (Amendment 3.1, 21 December 2016)	Revised Text (Version 4, 10 May 2017)	Justification for Change
		modification, or cessation (for efficacy) of the study beyond each interim analysis	

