
Section 13.1.8 Supportive Analysis
	
In order to address the risks associated with the inclusion of a long-term placebo arm, supportive analyses of the primary endpoint will compare clinical outcomes in the OCA treatment arm to historical controls.
 
By comparing how outcomes differ for treated subjects relative to historical controls, it is possible to estimate the effects of the treatment.
 
Although it might be relatively simple to assign a historical control based on a single observable characteristic, in practice, if the matching process is to successfully mitigate potential bias, it has to be done considering a full range of covariates across which the treatment and historical controls might differ.
 
Only covariates and not outcome variables will be included in the propensity score estimation. Therefore, there is no chance of biasing, to avoid biased results that are in favor of one treatment.
	
In order to address the risks associated with the inclusion of a long-term placebo arm, supportive analyses of the primary endpoint will compare clinical outcomes in the OCA treatment arm to historical controls, which serves as an external control for supportive analysis.
 
By comparing how outcomes differ for treated subjects relative to historical controls, it is possible to estimate the effects of the treatment between the treated subjects and the matched natural history subjects.
 
A full range of covariates across which the treatment and historical controls might differ will be considered to mitigate potential bias.
 
Only covariates and not outcome variables will be included in the propensity score estimation to avoid biased results that are in favor of one treatment.
 
The baseline characteristics between treated and natural history subjects in the matched dataset will be summarized and presented in a tabular format. Statistical methods such as Wilcoxon Rank-Sum test will be used to assess the balance for baseline covariates. The standardized difference and variance ratios for these covariates will also be calculated. In addition, box plots of propensity scores for treated and natural history subjects will be separately presented, to further assess the adequacy of matching.
 
A third-party statistician(s) will perform the propensity score modeling and matching. This
	
Clarifies the use of the historical controls as an external control in supportive analyses of the primary endpoint and clarify the process for selecting the comparator group for the primary efficacy analysis using propensity score analysis.
 
Clarifies the use of the historical controls as an external control in supportive analyses of the primary endpoint and clarify the process for selecting the comparator group for the primary efficacy analysis using propensity score analysis.

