5.5.2.3. Rationale for Control Groups

Placebo Control Group

The use of a randomized placebo control group added to established standard of care provides the best scientific evidence of efficacy and safety. The use of a placebo control provides a concurrent comparator group, accounting for not only a placebo effect but a standard of care effect. Notably, accounting for the standard of care effect is critical when designing an outcome-based study conducted globally when there are regional differences in the treatment of subjects with PBC.

Historical Control Group

The available robust historical PBC observational datasets (UK-PBC and Global PBC Study Group) will also be leveraged to provide further comparative evaluation of the clinical benefit of OCA. Each database includes >6000 patients with long-term follow-up.

Comparison of OCA treatment to the historical controls may provide utility in addressing potential bias or confounds associated with the placebo arm. For example, bias associated with the potential addition of commercial OCA and/or differences in long-term standard of care between the treatment arms including ancillary treatments and diagnostics.

Therefore, further evaluation of the effect of OCA will compare OCA treatment versus historical controls, and will be supportive to placebo comparisons (ie, comparisons to historical and placebo controls will be evaluated separately).

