13.1.1.1. Comparability of Historical Controls

Utilization of both historical control/observational databases (UK-PBC and Global PBC Study Group), with more than 6000 subjects each, allow for a rigorous subject level meta-analysis. The historical databases include long-term follow up, detailed subject-level information such as baseline clinical characteristics, longitudinal liver biochemistry, and long-term outcomes, and span a broad range of subject characteristics that may influence disease (disease state, age, gender, and regional differences in standard of care). Historical controls from both databases will be chosen based on the same study inclusion/exclusion criteria. Propensity score matching method will be utilized to select historical controls that match the treated subjects using available covariates. The adequacy of matching will be assessed by statistical methods described under [Section 13.1.8](#).

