13.1.8. Supportive Analysis

Per the International Conference on Harmonisation (ICH) E10 guidance, “where no obvious single optimal external control exists, it may be advisable to study multiple external controls”. In order to address the risks associated with the inclusion of a long-term placebo arm, supportive analyses of the primary endpoint will compare clinical outcomes in the OCA treatment arm to historical controls, which serves as an external control for supportive analysis.

In an attempt to avoid the inherent biases with historical controls and to maintain the integrity of this comparison, one can invoke matching methods to optimize comparability and find a historical control that is “similar” to a participating subject. The historical database control should be as similar as possible to the study population and should have been exposed to a similar standard of care (see [Section 5.5.2.3](#)).

A propensity score can be used to reduce bias through matching, stratification, regression adjustment, or some combination. Propensity scores use information from a pool of patients who do not participate in the study (historical controls) to identify what would have happened to participating subjects in the absence of the treatment. By comparing how outcomes differ for treated subjects relative to historical controls, it is possible to estimate the effects of the treatment between the treated subjects and the matched natural history subjects.

A full range of covariates across which the treatment and historical controls might differ will be considered to mitigate potential bias. Although the results of using matching controls are conditional only on the observed covariates, if one has the ability to measure many of the covariates that are believed to be related to the treatment assignment, then one can be fairly confident that approximately unbiased estimates for the treatment effect can be obtained. Both UK-PBC Group and the Global PBC Study Group formally collect numerous covariates that could be used for propensity score estimation including standard of care, eg, UDCA.

Historical controls will be chosen based on the same inclusion/exclusion criteria where possible. Propensity scores will be estimated using the available covariates that predict receiving the treatment. Only covariates and not outcome variables will be included in the propensity score estimation, to avoid biased results that are in favor of one treatment.

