The covariates and factors collected in the historical databases will be specified in the SAP.

Propensity scores will be estimated first through a logistic regression model with treatment group as the dependent variable and the above covariates/factors as independent variables. Then the stratum boundaries are determined based on the propensity score values for both groups (OCA population and control [historical and randomized placebo]) combined or in the OCA population or historical control group alone. Based on recommendations in the literature, quintiles of the estimated propensity score from the combined group will be used to determine the stratum boundary cut-offs for the different strata.

The baseline characteristics between treated and natural history subjects in the matched dataset will be summarized and presented in a tabular format. Statistical methods such as Wilcoxon Rank-Sum test will be used to assess the balance for baseline covariates. The standardized difference and variance ratios for these covariates will also be calculated. In addition, box plots of propensity scores for treated and natural history subjects will be separately presented, to further assess the adequacy of matching.

A third-party statistician(s) will perform the propensity score modeling and matching. This third-party statistician(s) will be separate and independent from the statistician(s) who will assess the success of matching and perform efficacy analyses. Outcome events collected in the historical database are: death (liver-related and all-cause), liver transplant, HCC, and other. Other is defined as cirrhosis or decompensation such as ascites, variceal bleed, and encephalopathy.

The propensity score quintile will be then be used as the stratification factor in the stratified log rank test to compare randomized OCA-treated subjects in the ITT population and historical controls (Overall Historical Control Population: both the UK-PBC Group and Global PBC Study Group databases) on the following outcomes:

- Time to death (all-cause)
- Time to liver-related death
- Time to liver transplant
- Time to liver transplant or death (all-cause)
- Time to liver transplant or liver-related death

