KM estimates of the distribution of the time-to-event will be tabulated and graphed by treatment group. The tabulation will include the KM estimate of the medians and corresponding 95% CIs if the medians can be estimated. The number and percent of subjects censored and with events will be presented. The hazard ratio and 95% CI will be determined based on a Cox regression model stratified by randomization strata to estimate the magnitude of the effect.

Sensitivity analyses will be conducted limiting to the separate individual historical control databases, ie, UK-PBC Group and Global PBC Study Group. To evaluate the robustness of the propensity score estimations, additional algorithms and factors may be considered.

Although the study is designed as a placebo-controlled study, the DMC may recommend changes to study conduct based on the pre-specified interim analyses (see [Section 13.1.12](#)), including the potential use of a revised primary efficacy analysis. This analysis would compare all subjects in the OCA population, to all control subjects (randomized placebo and historical controls) on time to liver transplant or death (all-cause), using similar statistical methodology as specified above.

Notably, the planned primary analysis would not be revised without prior agreement with regulatory authorities.

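### Section 13.1.8 compares OCA with historical controls, and allows placebo to be pooled with them, but never directly tests whether randomized placebo subjects and those controls have similar outcomes

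*Protocol*

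**What the plan says.** All references are to the current protocol, Version 6.

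- **Supportive comparison (13.1.8).** "supportive analyses of the primary endpoint will compare clinical outcomes in the OCA treatment arm to historical controls, which serves as an external control". The log-rank test, stratified by propensity-score quintile, is used "to compare randomized OCA-treated subjects in the ITT population and historical controls" on five outcomes built from death, liver-related death and liver transplant. Placebo is not a comparison group. It is mentioned only as part of the combined control group when the stratum boundaries are set.
- **Selection of controls (13.1.1.1).** "Propensity score matching method will be utilized to select historical controls that match the treated subjects using available covariates".
- **Checks on the matching (13.1.8).** Wilcoxon tests, standardized differences and variance ratios on baseline covariates, and box plots of propensity scores, for treated versus natural history subjects. Sensitivity analyses repeat the comparison in each database separately, and other propensity algorithms may be considered.
- **Acknowledged limit (13.1.8).** "the results of using matching controls are conditional only on the observed covariates".
- **Definition of the control population (13.1.1).** Historical subjects must be shown to be comparable with randomized subjects in their characteristics and in how their disease progresses. No method is given for progression.
- **Relation between the two comparisons (5.5.2.3).** "comparisons to historical and placebo controls will be evaluated separately". The historical comparison "may provide utility in addressing potential bias or confounds associated with the placebo arm", with added commercial OCA as an example.
- **Possible revised primary analysis (13.1.8).** "This analysis would compare all subjects in the OCA population, to all control subjects (randomized placebo and historical controls"), on time to liver transplant or all-cause death. Prior agreement with regulatory authorities is required.

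**The concern.** Matching on measured covariates cannot remove differences in willingness to join a trial, intensity of specialist follow-up, calendar era or access to transplant. Any of these could make trial subjects do better than registry subjects without a drug effect.

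The trial already contains a group that bears on this. Randomized placebo subjects passed the same selection and receive the same trial care as OCA subjects. Before any commercial OCA use, and if matching has worked, their hazard ratio against the same historical controls should be near 1. The protocol does not plan that comparison.

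Two things are at stake. A trial-versus-registry difference could be read as support for OCA. And if the revised primary analysis were adopted, the same difference would enter the control group directly, with no stated check that the two components have similar event rates.

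**Working it through.** **1. The plan's own figures.** The point disputes none of them, and they reproduce. For hazard ratio (HR) 0.60, two-sided 5% and 80% power, the Freedman formula gives 126 events. With Lan-DeMets O'Brien-Fleming looks at 64 and 96 events, power at 127 events is 81.3%. Exponential survival with 4 years' accrual and 10 years in total gives event probabilities of 0.398 (placebo) and 0.263 (OCA), mean 0.331. Then 127/0.331 = 384, and 384/0.90 = 427, against the stated 428. The proposed change leaves these figures alone.

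**2. Requirement against checks.** Section 13.1.1 asks for comparability with randomized subjects (both arms) in characteristics and progression. Sections 13.1.1.1 and 13.1.8 match to treated subjects and examine baseline covariates and propensity scores. The per-database analyses compare OCA with one registry at a time, so a difference shared by both registries remains. None of these steps examines outcomes in untreated trial subjects against outcomes in the registries.

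**3. Illustration of size.** From the protocol: 428/2 = 214 per arm, less 10% = 193; follow-up 6 to 10 years, mean 8. Assumed, because the protocol gives no value: 8-year registry risk of death or transplant 10% to 20%; 1:1 or 1:2 matching; trial-versus-registry hazard ratio h = 0.7; no OCA effect.

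Expected events are approximately n × risk in the registry and 193 × [1 − (1 − risk)^h] in a trial arm. The standard error (SE) of the log hazard ratio is √(1/d₁ + 1/d₂). The probability of a false benefit is Φ(−ln h / SE − 1.96).

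- Risk 10%, 1:1: registry 193 × 0.10 = 19 events; OCA 193 × (1 − 0.9^0.7) = 14. SE = √(1/19 + 1/14) = 0.352. Φ(0.357/0.352 − 1.96) = Φ(−0.95) = 0.17.
- Risk 20%, 1:2: registry 386 × 0.20 = 77 events; OCA 193 × (1 − 0.8^0.7) = 28. SE = √(1/77 + 1/28) = 0.221. Φ(0.357/0.221 − 1.96) = Φ(−0.34) = 0.37.

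Simulation under the same assumptions gave 17% to 36%, against a nominal 2.5%. It gave 9% to 18% at h = 0.8 and 27% to 61% at h = 0.6. With placebo pooled into the control group, the false-benefit rate at h = 0.7 was 7% to 20%. OCA versus placebo stayed at 2.2% to 2.8%.

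Using the planning hazards of the primary composite instead, with 214 to 1000 historical controls, h = 0.7 gives 67% to 83%. That composite includes MELD and decompensation events that are not among the five historical outcomes, so these figures mainly show how strongly the result depends on the assumed event rate.

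**4. How well the proposed check would work.** With no drug effect, placebo versus historical has the same expected hazard ratio and the same SE as OCA versus historical. At HR 0.70 the 95% CI is 0.70 × exp(±1.96 × SE):

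- SE 0.352: 0.35 to 1.40
- SE 0.221: 0.45 to 1.08

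Both intervals include 1.

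**5. A ratio of the two hazard ratios adds little.** (OCA/historical) ÷ (placebo/historical) ≈ OCA/placebo, which the protocol already estimates.

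**The case against.** The strongest case against is that this is an extra sensitivity contrast for an analysis labelled supportive, of a kind often left to the SAP, which is not at hand. The historical comparison lies outside the testing hierarchy in Section 13.1.10, so it does not affect study-wise type I error. The revised primary analysis would need regulatory agreement. These points stand and limit the weight of the finding. They do not remove it, because the protocol itself fixes the comparison groups, the matching target and the possible pooling, and Section 13.1.1 sets a requirement that the stated checks do not meet.

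Two stronger readings are tempting, and neither is supported.

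- **That a bias would go undetected.** Transplant or death is analysed for OCA against placebo (13.1.4) and against historical controls (13.1.8). A gap between the two hazard ratios would be an indirect signal. The difficulty is its interpretation. Section 5.5.2.3 justifies the historical controls by possible bias in the placebo arm, so the gap could be put down to commercial OCA when its source is selection or era.
- **That placebo versus historical would reliably expose the bias.** The intervals in step 4 show that it would not do so for a 30% difference. The placebo arm may also be affected by commercial OCA, and cutting follow-up when that starts may be informative.

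**Conclusion.** The point holds as a cheap improvement. The protocol compares OCA with historical controls and permits pooling them with placebo, but does not directly test similarity of outcomes between randomized placebo and historical controls. A selection or era difference is therefore not directly tested, and it can be confused with placebo contamination.

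The false-benefit rates are illustrative only: the size of the bias, the registry risk and the matching ratio are all assumed, and only bias in favour of OCA was examined. The primary OCA-versus-placebo analysis is unaffected. The conclusion rests on the protocol alone; the SAP may already add this comparison.

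**What to change.** In Section 13.1.8:

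1. Match historical controls to all randomized subjects, blind to arm, so that one matched set serves both comparisons.
2. Run the same propensity-stratified analysis for randomized placebo versus historical controls on the same five outcomes. Report its hazard ratio and 95% CI beside the OCA-versus-historical result. Do not add a ratio of the two.
3. Use full placebo follow-up as the main version. Add a sensitivity version cut at the start of commercial OCA, noting that this censoring may be informative.
4. State that the comparison is imprecise and that a CI including 1 does not establish comparability.
5. Require this comparison to be reviewed before any analysis that pools placebo with historical controls.

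The change should be fixed before propensity scores are determined and treatment is unblinded, the same deadline that Section 13 sets for the SAP. It costs a few sentences and a further run of an analysis already planned. It needs no new patients or data, and 127 events and 428 subjects are unchanged. The drawback is an imprecise estimate that may make the historical result look less favourable.

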APPENDIX I. SUMMARY OF CHANGES: PROTOCOL VERSION 3 TO PROTOCOL VERSION 4 (DATED 10 MAY 2017)

Please note that Protocol 747-302 Version 3.1 was generated to specifically address US FDA post-marketing requirements but was not submitted to other Regulatory/Competent Authorities or Ethics Committees due to ongoing negotiations. Therefore, a full accounting of the changes from Protocol Version 3 to Protocol Version 4 is provided below.

Rationale and Summary of Changes

Major revisions to Protocol 747-302 include the modification of inclusion/exclusion criteria to expand the PBC disease spectrum, the addition of progression to cirrhosis as a secondary endpoint, and the addition of 2 interim analyses. Additional revisions include an increase in subject number and the number of required clinical outcome events, a change in the study phase, an update to the nomenclature for PBC, and various clarifications within the protocol.

[figure not shown]
[figure not shown]
The text deleted from Protocol Version 3 is crossed out while revised text in Version 4 is indicated in bold font. Minor/editorial changes and non-substantial changes are not listed individually. For efficiency, rationales that impact multiple sections are provided below and referenced in the table with the corresponding rationale number.

1. **The phase of the study has been changed from “3b” to “4”** to reflect that this is a post-marketing study. Protocol 747-302 is considered a Phase 4 study in regions where OCA has received regulatory approval for PBC, ie, in the US and the EU. In all other regions, this study is considered Phase 3b. In May 2016, the FDA granted accelerated approval for OCA (Ocaliva) for the treatment of PBC. In December 2016, Ocaliva received Conditional Approval from the European Medicines Agency’s Committee for Medicinal Products for Human Use.
2. **The term “primary biliary cirrhosis”** has been changed to “primary biliary cholangitis” to reflect recent changes in the nomenclature for PBC.
3. **The number of required adjudicated events for the final analysis has increased** from 121 to 127 due to the addition of two interim analyses, which will allow an independent DMC to recommend continuation, modification, or cessation (for efficacy) of the study. One interim analysis will occur at 50% information (after 64 events occur) and one at 75% information (after 96 events occur). In addition, inclusion of PBC subjects with earlier stage disease will increase the time to event, thereby requiring more events to maintain follow-up to approximately 6 years.
4. The first-year study enrollment rate was lower than projected due to slower-than-anticipated activation of sites and required a re-estimation of the accrual duration. Using observed accrual rates, the accrual duration was extended by 2 years. The follow-up period was maintained at 6 years, thereby leading to a total trial duration of 10 years.

5. “**Encephalopathy**” has been modified to “Hepatic Encephalopathy” to clarify that the relevant Clinical Outcome Event should be related to hepatic disease.
6. **Hepatocellular carcinoma (HCC)** has been redefined as a secondary endpoint instead of a component of the primary composite-event endpoint per Regulatory Authority request.
7. Histological confirmation (biopsy) has been added as an acceptable method of confirming a diagnosis of HCC.
8. **Broadening the Spectrum of Disease:** Lowering the minimum allowable baseline ALP from $>5x$ ULN to $>3x$ ULN and raising the maximum allowable baseline total bilirubin to $\leq 5x$ ULN will increase the number of subjects enrolled with early and advanced disease facilitating the collection of safety and efficacy data in a population that covers the spectrum of PBC disease and overlaps with the subject population in the Phase 3 protocol 747-301. However, to ensure enrollment of an adequate number of subjects with abnormal total bilirubin, a minimum of 30% of the subjects enrolled in the study will have elevated bilirubin ($>ULN$) at Screening.
9. The titration regimen has been updated to reflect assessment of both tolerability and biochemical response prior to up-titration per the USPI and SmPC.
10. The increase in enrollment from 350 to 428 subjects is due in part to the increased number of events from two additional interim analyses, and in part due to the change in the estimated placebo baseline hazard rate, which resulted from changing the lower limit of ALP from $>5x$ ULN to $>3x$ ULN in the enrollment criteria #2.
11. **Progression to Cirrhosis** has been added as a secondary endpoint: Due to the chronic nature of PBC, outcomes require a very long time to accrue to evaluate the impact of potential therapies. Despite the proven prognostic utility of ALP and bilirubin, there is a remaining need to evaluate noninvasive assessments of disease progression that can be linked to histological progression of the disease. Therefore, it is important to evaluate potential noninvasive markers of fibrosis/cirrhosis and their relationship to clinical outcomes as part of Study 747-302.
12. **A Per Protocol (PP) population** has been added to the statistical analysis section. Sensitivity analysis for primary efficacy endpoints and key secondary efficacy endpoints will be performed using PP population.

Section	Original Text (Amendment 3, 07 September 2016)	Revised Text (Version 4, 10 May 2017)	Justification for Change

Title Page Synopsis, Title of Study
	
A Phase 3b, Double-Blind, Randomized, Placebo-Controlled, Multicenter Study Evaluating the Effect of Obeticholic Acid on Clinical Outcomes in Subjects with Primary Biliary Cirrhosis
	
A Phase 4, Double-Blind, Randomized, Placebo-Controlled, Multicenter Study Evaluating the Effect of Obeticholic Acid on Clinical Outcomes in Subjects with Primary Biliary Cholangitis
	
Rationale 1 and 2

Study Personnel Contact Information
	
Or if Not Available:
 
Contact: PPD [redacted] MD, PhD, Executive Director, Clinical Research, Intercept Pharmaceuticals, Inc.
 
Telephone: PPD [redacted]
 
Mobile: PPD [redacted] (Pacific time zone)
 
Email: PPD [redacted] PPD [redacted]
 
Clinical Operations and Project Management
 
Contact: PPD [redacted] PPD [redacted] Clinical Operations, Intercept Pharmaceuticals, Inc.
 
Telephone: PPD [redacted] (Pacific time zone)
 
Mobile: PPD [redacted]
 
Fax: PPD [redacted]
	
O
	
The contact information of clinical operations and project managements personnel is no longer required per Sponsor's procedures.

Section	Original Text (Amendment 3, 07 September 2016)	Revised Text (Version 4, 10 May 2017)	Justification for Change
	
Email: PPD [redacted] PPD [redacted]
		

Synopsis, Studied Period (Years)
	
The study is event driven and total duration will be determined by the time required to accrue approximately 121 primary endpoint events, estimated to be approximately 8 years. Subjects are expected to have a minimum follow-up time of approximately 6 years.
	
The study is event driven and total duration will be determined by the time required to accrue approximately 127 primary endpoint events, estimated to be approximately 10 years. Subjects are expected to have a minimum follow-up time of approximately 6 years.
	
Rationale 3 and 4

Synopsis, Phase of Development
	
Phase 3b
	
Phase 4
	
Rationale 1

Synopsis, Objectives, Primary, Statistical Methods – Efficacy Analyses Section 6.1 Primary Objective Section 11.1.1 Primary Assessments Section 13.1.3 Primary Efficacy Analysis
	
 Encephalopathy (as defined by a West Haven score of ≥ 2) Hepatocellular carcinoma confirmed by 2 complimentary imaging modalities 	
 Hepatic encephalopathy (as defined by a West Haven score of ≥ 2) 	
Rationale 5 Rationale 6

Synopsis, Objectives, Secondary
	
To assess the effect of OCA compared to placebo on time to first occurrence of each individual
	
To assess the effect of OCA compared to placebo on time to first occurrence of each individual
	
Rephrasing the objective

Section	Original Text (Amendment 3, 07 September 2016)	Revised Text (Version 4, 10 May 2017)	Justification for Change

Section 6.2 Secondary Objectives
	
component of the primary endpoint as listed above and also to include liver related death.
 
Insertion
 
To assess the pharmacokinetics of OCA and its conjugates in a subset of subjects
	
component of the primary endpoint as listed above.
 
To assess the effect of OCA compared to placebo on time to occurrence of liver-related death.
 
To assess the effect of OCA compared to placebo on progression to cirrhosis.
 
To assess the effect of OCA compared to placebo on time to occurrence of hepatocellular carcinoma (HCC).
 
To characterize the pharmacokinetics of OCA and its conjugates in a subset of subjects
	
Rationale 11
 
Rationale 6

Synopsis, Methodology:
 
Schematic Diagram
 
Section 7.1.1 Study Design Diagram, Figure 1
	 
Initial dose titration of investigational product should occur at the Month 3 visit, or any study visit thereafter for subjects on all dosing regimens, based on tolerability.
 
 Subjects should titrate to a maximum dose of 10-mg OCA once daily (or matching 	
A minimum of 30% of subjects will have elevated bilirubin (>ULN) at Screening.
  
Initial dose titration of investigational product should occur at the Month 3 visit, or any study visit thereafter for subjects on all dosing regimens, based on tolerability and biochemical response (up-titration should be considered when ALP and/or total bilirubin are >ULN).
 
 Subjects should titrate to a maximum dose of 10-mg OCA once daily (or matching placebo) at the Month 3 visit or at any study 	
Rationale 8
 
Rationale 8
 
Rationale 9

Section	Original Text (Amendment 3, 07 September 2016)	Revised Text (Version 4, 10 May 2017)	Justification for Change
	
placebo) at the Month 3 visit or at any study visit following the Month 3 visit based on tolerability of the product.
 
 Subjects classified as Child-Pugh Class B should eventually titrate to a maximum dose of 5-mg OCA or matching placebo once daily, based on tolerability. Subjects classified as Child-Pugh Class C should titrate to a maximum dose and frequency of 10-mg OCA or matching placebo twice weekly, based on tolerability. 
Planned Dosing Regimen by Cirrhosis and Child-Pugh Score (Table)
 
^b Planned titration regimen is shown; however, the titration of dose and/or frequency is dependent on subject tolerability, and/or changes in cirrhosis status or Child-Pugh Score at any time during the study.
	
visit following the Month 3 visit based on tolerability and biochemical response of the product.
 
 Subjects classified as Child-Pugh Class B should eventually titrate to a maximum dose of 5-mg OCA or matching placebo once daily, based on tolerability and biochemical response. Subjects classified as Child-Pugh Class C should titrate to a maximum dose and frequency of 10-mg OCA or matching placebo twice weekly, based on tolerability and biochemical response. 
Planned Dosing Regimen by Cirrhosis and Child-Pugh Score (Table)
 
^b Planned titration regimen is shown; however, the titration of dose and/or frequency is dependent on subject tolerability, biochemical response, and/or changes in cirrhosis status or Child-Pugh Score at any time during the study.
	

Synopsis, Number of Subjects (Planned)
 
Section 7.2 Number of Subjects
	
Insertion
 
Change in Synopsis section
 
Approximately 350 subjects
	
In the event additional subjects are needed for the enrollment in the biopsy substudy (N = 45 subjects, as defined in Addendum 2), subjects who agree to participate in the sub study may be added to the target subject enrollment number currently planned.
 
Approximately 428 subjects are planned to be enrolled in the study.
	
Rationale 10 and Addendum 2

Section	Original Text (Amendment 3, 07 September 2016)	Revised Text (Version 4, 10 May 2017)	Justification for Change
	
Change in Section 7.2 section
 
It is expected that approximately 350 subjects will be randomized in the study to achieve 121 adjudicated primary endpoint events.
	
It is expected that approximately 428 subjects will be randomized in the study to achieve 127 adjudicated primary endpoint events.
	

Synopsis, Inclusion Criteria
 
Section 8.2 Subject Inclusion Criteria
	
2. A mean total bilirubin >ULN and $\leq 3x$ ULN and/or a mean ALP >5x ULN
	
2. A mean total bilirubin >ULN and $\leq 5x$ ULN and/or a mean ALP >3x ULN
	
Rationale 8

Synopsis, Inclusion Criteria
 
Section 8.2 Subject Inclusion Criteria
	
5. Contraception: Female subjects must be postmenopausal, surgically sterile, or if premenopausal (and not surgically sterile), be prepared to use ≥ 1 effective method of contraception during the study and for 30 days after the end of treatment visit. Effective methods of contraception are considered to be those listed below:
 
 • Double barrier method, ie, (a) condom (male or female) or (b) diaphragm, with spermicide; or • Intrauterine device (IUD); or • Vasectomy (partner); or • Hormonal (eg, contraceptive pill, patch, intramuscular implant or injection); or • Abstinence, if in line with the preferred and usual lifestyle of the subject 	
5. Contraception: Female subjects of childbearing potential must use ≥ 1 effective method of contraception during the study and until 30 days following the last dose of investigational product. Effective methods of contraception are considered to be those listed below:
 
 • Barrier method, ie, (a) condom (male or female) or (b) diaphragm, with spermicide • Intrauterine device (IUD) • Vasectomy (partner) • Hormonal (eg, contraceptive pill, patch, intramuscular implant or injection) • Abstinence, if in line with the preferred and usual lifestyle of the subject 	
Standardizing language across protocols; removing double-barrier terminology.

Section	Original Text (Amendment 3, 07 September 2016)	Revised Text (Version 4, 10 May 2017)	Justification for Change														

Synopsis, Exclusion Criteria
 
Section 8.3 Subject Exclusion Criteria
	
2. Presence of clinical complications of PBC or clinically significant hepatic decompensation, including:
 
3. Mean total bilirubin >3x ULN
	
2. Presence of clinical complications of PBC or clinically significant hepatic decompensation, including:
 
•History of liver transplant, current placement on a liver transplant list, or current MELD score >12. Subjects who are placed on a transplant list despite a relatively early disease stage (for example per regional guidelines) may be eligible as long as they do not meet any of the other exclusion criteria
 
3. Mean total bilirubin >5x ULN
	
This criterion (sub-bullet) is already included in Version 3 of the protocol. In the Version 4, it is added to the synopsis for consistency.
 
Rationale 8
														

Synopsis, Duration of Treatment
	
It is estimated that subjects will be followed up for a minimum of 6 years. The study is event driven and total duration of treatment will be determined by the time to accrue 124 total primary endpoint events.
	
It is expected that subjects will be followed up for a minimum of 6 years. The study is event driven and total duration of treatment will be determined by the time to accrue 127 total primary endpoint events.
	
Rationale 3
														
